eCRF	Electronic case report form
ER	Extended release
H&E	Hematoxylin and eosin
HADS	Hospital Anxiety and Depression Score
HCG	Human chorionic gonadotropin
HCl	Hydrochloride
HR	Heart rate
IFSI	International Forum for the Study of Itch
KOR	Kappa opiate receptor
LDH	Lactate dehydrogenase
LOV	Last observed value
MedDRA	Medical Dictionary for Regulatory Activities
mL	Milliliter
MOR	Mu opiate receptor
MOS	Medical Outcomes Study
NRS	Numerical Rating Scale
OV	Observation Period Visit
PAS	Prurigo Activity Score
PBI-P	Patient Benefit Index, pruritus version
PD	Pharmacodynamics
PK	Pharmacokinetics
PRO	Patient-Reported Outcome
PT	Preferred term
QoL	Quality of life
RR	Respiratory rate
SAE	Serious adverse event
SAP	Statistical analysis plan
SAS	SAS [®] statistical software
SBP	Systolic blood pressure
SD	Standard deviation
SOC	System organ class
SOWS	Subjective Opiate Withdrawal Scale
TEAE	Treatment-emergent adverse events
TV	Treatment Period Visit

US	United States
UV	Ultraviolet light
UV-B	Ultraviolet light – B
VRS	Verbal Rating Scale
WHO	World Health Organization

1. Introduction

Protocol TR03ext is being conducted to examine the safety and anti-pruritic efficacy of nalbuphine hydrochloride (HCl) extended release (ER) tablets in prurigo nodularis patients. The purpose of this statistical analysis plan (SAP) is to provide specific guidelines from which the analysis will proceed. It will describe in detail the algorithms and conventions to be used in the analysis and presentation of the efficacy and safety data for protocol TR03ext. Any deviations from these guidelines will be documented in the clinical study report (CSR). In the event where discrepancies in statistical analysis may be encountered between the SAP and what is described in the study protocol, the SAP will take precedence.

2. Objectives

2.1. Primary Objectives

The primary objective of the study is to evaluate the safety and tolerability of nalbuphine HCl ER tablets during a treatment period of up to 50 weeks.

2.2. Secondary Objectives

The secondary objectives of the study are:

- To evaluate the safety of nalbuphine by achieved maintenance dose at the end of Treatment Week 4,
- To assess skin lesion improvement using the metrics of the Prurigo Activity Score (PAS),
- Change from Baseline in Patient-Reported Outcome (PRO) measures Worst (i.e. most severe itching over the past 24 hours) itch Numerical Rating Scale (NRS), average itch intensity NRS, Verbal Rating Scale (VRS) (itchy, burning and stinging), Medical Outcomes Scale (MOS) Sleep-R, ItchyQol, and Hospital Anxiety and Depression Score (HADS) by the final Treatment Period Visit,
- Change between Baseline and the final Treatment Period Visit in Patient Benefit Index, pruritus version (PBI-P),
- A description of the percentage of patients utilizing various doses of nalbuphine HCl ER tablets by Study Week,
- A description of the frequency and reasons for dose up-and down-titration and treatment discontinuation during the study,

- Frequency and distribution by time on study of patients determined to meet failure-to-improve criteria,
- Changes in the PRO measurements during the Washout Period after cessation of treatment of nalbuphine HCl ER tablets,
- Time to first use of rescue medications and the number of days of use of rescue medications for itching,
- To evaluate the daily changes in the Subjective Opiate Withdrawal Scale (SOWS) during the Washout Period after cessation of treatment of nalbuphine HCl ER tablets.

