The maximum dose the patient should reach at the end of Week 2 is 120 mg BID. If this dose is tolerated (as determined by the TC2 assessment), an additional up-titration may be attempted during Week 3.

The maximum dose the patient should reach at the end of Week 3 is 180 mg BID. If this dose is tolerated, it should be maintained throughout Week 4.

The dose achieved as of the end of Treatment Week 4 will be maintained throughout the rest of the Treatment Period. This dose will be defined as the patient's "maintenance dose".

During Treatment Weeks 1-4, the decision to up-titrate the patient's dose should be made based on tolerance to study drug. If the tolerance level becomes unacceptable to either the patient or the Investigator, the dose should be reduced incrementally until tolerance is stabilized (reduce dose by 30 mg BID if at the 30 mg, 60 mg, 90 mg or 120 mg dose level and reduce by 60 mg BID if the patient is at the 180 mg dose level). Patients who do not tolerate the 180 mg BID should be down titrated to the 120 mg BID dose level and maintained there if stabilized.

Two single dose reductions or dose holds per patient is permitted during Treatment Period at the Investigator's discretion. If subsequent dose reductions or dose interruptions are needed, the Medical Monitor must be contacted. The duration of any dose hold must be discussed with the Medical Monitor.

4. Statistical Considerations

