4.6.2. Safety

The Safety population will consist of all enrolled patients who have received a single dose of study medication in the TR03 extension study. The Safety population will be used to evaluate the safety and efficacy endpoints defined for this study.

Patients will be summarized in a single nalbuphine treatment group.

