4.9. Examination of Subgroups

No *a priori* planned subgroup analyses are specified and none will be performed.

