4.10. Data Display Treatment and Other Descriptors

Unless otherwise noted, TR03 extension study treatments will be presented in all tables, listings and figures (TLFs) as: All Patients. Additionally, TR03 core study randomized treatments will be presented as: Nalbuphine 90 mg, Nalbuphine 180 mg, and Placebo.

For measurements collected at multiple study visits, visit and week number will be used in all TLFs. Baseline results (as described in Section [4.2](#)) will be displayed as “Baseline.”

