4.11. Changes in the Planned Analysis

Section 9.7.7.5 of the protocol discusses a 9-item sleep problems index that can be generated for the MOS Sleep Scale-R. This, however, will not be implemented. SAP [Section 8.1.6](#) describes the summaries that will be presented for the MOS Sleep Scale-R.

Section 19.6 of the protocol states that opioid medication usage will be tabulated separately from all other concomitant medications. Instead, opioid medication usage will be tabulated with all other concomitant medications as discussed in SAP Section [7.1](#).

Section 19.7 of the protocol states that mean dose during the treatment period will be summarized. Instead, as discussed in SAP Section [7.3.1](#), highest dose achieved during the treatment period will be summarized.

[Section 8.6](#) of the SAP describes the summarization and graphical presentation of premature discontinuation due to lack of efficacy or adverse events. This is not included in the protocol but is desired for reporting purposes.

5. Patient Disposition

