 - If the month and year are the same as the month and year of the first dose of study drug, and the end date (after any imputation) is on or after the first dose of study drug, then use the date of the first dose of study drug as the imputed onset date.
 - If the month and year are the same as the month and year of the first dose of study drug, and the end date (after any imputation) is prior to the date of the first dose of study drug, then use the end date as the imputed onset date.
- If the month is missing but the year is known (day can be either missing or known):
 - If the year is different from the year of the first dose of study drug then use Jan. 1st of the reported year as the imputed onset date.

- If the year is the same as the year of the first dose of study drug and the end date (after any imputation) is on or after the first dose of study drug then use the date of the first dose of study drug as the imputed onset date.
- If the year is the same as the year of the first dose of study drug and the end date (after any imputation) is prior to the date of the first dose of study drug, then use the end date as the imputed onset date.
- If the start date is completely missing, the event is assumed to be treatment-emergent.

For incomplete AE end dates:

- If the day is missing but the month and year are known then use the last day of the month as the imputed end date.
- If the month is missing but the year is known (and the day is either missing or known) then use Dec. 31st of the year as the imputed end date.

Adverse events will be coded according to MedDRA (version to be delineated in the clinical study report).

All AE summary tables will present system organ class (SOC) and preferred term (PT), will include counts of patients, and will be based on TEAEs. SOC will be displayed in descending order of frequency overall and then alphabetically. PT will be displayed in descending order of frequency overall and then alphabetically within SOC. A patient with two or more AEs within the same level of summarization will be counted only once in that level using the most extreme incident. Percentages will be based on the number of patients in the safety population.

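### Safety by Week 4 maintenance dose is a stated secondary objective, but the SAP specifies no analysis that answers it

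*SAP*

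**What the plan says.** The first secondary objective in SAP Section 2.2 is "To evaluate the safety of nalbuphine by achieved maintenance dose at the end of Treatment Week 4". Section 3.4 supplies the grouping variable: "The dose achieved as of the end of Treatment Week 4 will be maintained throughout the rest of the Treatment Period", and it names that dose the maintenance dose. Titration in Weeks 1 to 4 is by tolerability, to a final dose between 30 mg and 180 mg BID.

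The presentation rules point elsewhere. Section 4.6.2: "Patients will be summarized in a single nalbuphine treatment group". Section 4.9 states that no a priori "planned subgroup analyses are specified and none will be performed". Section 4.10: "TR03 extension study treatments will be presented in all tables, listings and figures (TLFs) as: All Patients", followed by "Additionally, TR03 core study randomized treatments will be presented as: Nalbuphine 90 mg, Nalbuphine 180 mg, and Placebo". For adverse event tables, Section 9.1 sets the denominator: "Percentages will be based on the number of patients in the safety population".

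Achieved dose is used in two places outside safety. Section 7.3.1 counts patients at each dose by visit from Visit 3/Week 5, and by highest dose. Section 8.3 counts dosing changes by reason.

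**The concern.** An objective with a defined grouping variable should lead to an endpoint and at least one planned table. Here the chain stops at the objective. This is a safety extension, so how tolerability over the following months relates to the dose on which a patient settled is a central descriptive question, and the SAP itself poses it.

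If the gap stays, there are two outcomes. The study report may be silent on a stated objective. Or tables by dose may be built after the data are seen, with dose groups, denominator and time window chosen at that point. Either is avoidable at little cost while the plan can still be changed.

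**Working it through.** No formula applies. The SAP gives no sample size and plans no inference (Section 4.3), so the check is whether the objective can be traced to an output.

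1. **Objective to endpoint.** Section 2.2 lists ten secondary objectives: safety by maintenance dose, PAS, PRO change, PBI-P, doses by week, titration and discontinuation, failure to improve, PRO change in washout, rescue medication and SOWS. Section 3.3.2 lists nine endpoints. Matching them one to one leaves 10 − 9 = 1 objective without an endpoint, and it is safety by maintenance dose.

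2. **Endpoint to columns.** Sections 4.6.2 and 4.10 give one extension column plus the parent-study arms. The parent-study arm was assigned at randomization in the earlier trial. The maintenance dose is reached by fresh titration from 30 mg in this one. The first cannot serve as the second.

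3. **Columns to tables.** The safety outputs in Section 9 break down as follows:
   - 9.1.1 to 9.1.5: SOC and PT, relationship, severity, study period, discontinuation and seriousness.
   - 9.1.6 and 9.1.7: the same kinds of split, plus gender.
   - 9.2.1 (SOWS): by day, and by treatment group for the change and maximum scores. With one treatment group set in 4.6.2, that phrase cannot mean maintenance dose.
   - 9.2.2 to 9.5: neurological, laboratory, vital sign and physical examination outputs, with no dose split.

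   Safety summaries by maintenance dose: 0.

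4. **Dose outputs.** Sections 7.3.1 and 8.3 show how many patients were at each dose and why doses changed. Neither cross-classifies an adverse event, laboratory value or vital sign by dose.

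5. **Recorded changes.** Section 4.11 lists four departures from or additions to the protocol: the sleep index, opioid tabulation, the dose summary, and discontinuation displays. This objective is not among them.

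The time window for the fix follows from the SAP's own definitions. The Titration Period in Section 9.1 runs to first dose date + 27 days. Under the study-day rule in 4.2 that is day 27 + 1 = 28, so events after Week 4 start on day 29. That also matches the start of the Weeks 5 to 50 window of the primary endpoint in 3.3.1.

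**The case against.** The strongest reply is that this is a single-arm, open-label, descriptive study in which dose is titrated on tolerability. Tables by dose cannot support a dose-response claim, and the primary endpoint does not need them. Those facts stand, and they limit how the tables may be read. They do not explain why an objective is stated and then left without an output.

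Three stronger readings are tempting, and the SAP does not support them.

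- **That Section 4.9 forbids any split by dose.** It speaks of subgroup analyses, and the same SAP plans descriptive breakdowns by gender (9.1.6, 9.1.7), by parent-study arm (8.1) and by treatment duration (8.1.3, 8.1.5, 8.1.8). The defect is an omission. Those splits also show that descriptive breakdowns are feasible here.
- **That highest dose has been put in place of maintenance dose, so that patients who stepped down are misclassified.** Section 4.11 does say that "highest dose achieved during the treatment period will be summarized" instead of mean dose, but that is a declared change to the dosing summary. Section 7.3.1 also tabulates achieved dose at each visit from Week 5, and no safety table is grouped by highest dose.
- **That the sponsor will have no description of safety by dose at all.** ECG and PK/PD analyses go to separate plans, and the table shells and protocol are not shown. What can be said is that this SAP specifies none. The separate plans are described as covering ECG and PK/PD only, not the adverse event, laboratory and vital sign summaries governed here.

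**Conclusion.** The gap is real and should be closed. One of ten secondary objectives has no endpoint and no planned output in this SAP, and its omission is not recorded as a decision. The permitted maintenance doses span 30 to 180 mg BID, a ratio of 180/30 = 6, all shown in one column. That ratio is the allowed range only. The SAP gives neither a sample size nor an expected spread of doses, so the amount of safety information lost cannot be sized.

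The conclusion rests on the SAP alone. Section 1 gives the SAP precedence over the protocol where they differ on analysis, but a table shell that is not shown could already carry the split. If so, the SAP text still needs to say so.

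**What to change.** Add safety by Week 4 maintenance dose to the endpoints in 3.3.2, and amend 4.6.2, 4.9 and 4.10 to allow this descriptive grouping. In 9.1, specify these tables by maintenance dose: TEAE overview, SOC/PT, SAEs, AEs leading to discontinuation and AEs of special interest. Set the rules in advance:

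- **Groups:** fixed dose categories, with a stated rule for combining sparse levels. The category list in 7.3.1 runs to 210 mg BID while the titration text in 3.4 stops at 180 mg BID. The two must be reconciled before groups are set.
- **Denominator:** patients still on drug at the end of Week 4. Those who stopped earlier have no maintenance dose and should be reported separately.
- **Window:** onsets from day 29, with washout events shown separately and patient-years given. For patients who stop drug early but stay on study, 9.1 counts every AE from first dose onward as Treatment Period, so these tables need their own rule for separating washout.
- **Classification:** by the Week 4 dose, whatever dose changes follow, since 3.4 allows later reductions and holds.
- **Interpretation:** a statement that dose was titrated on tolerability, so the tables are descriptive and not a dose-response comparison.

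If the objective is no longer wanted, record in 4.11 that it is dropped.

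The cost is SAP wording and modest programming: new columns on tables already planned, plus the at-risk set, window and patient-years. The downside is small cells at some doses.

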2.3. Exploratory Objectives

The exploratory objective of the study is to evaluate the potential of nalbuphine HCl ER tablets impact on the measurement of nerve fiber density (histology) and mu opiate receptor (MOR)/kappa opiate receptor (KOR) density (histology, Western Blot), as well as histological hematoxylin and eosin (H&E) changes in skin biopsies taken at Baseline and by the final Treatment Period Visit to investigate possible correlation with any clinical response and also compared to biopsy material assessed during study TR03 (optional procedures at select sites only).

3. Investigational Plan

3.1. Overall Study Design and Plan

This is an open label safety and tolerability extension study for patients who have completed the TR03 study. Patients will either enter directly into a drug Treatment Period (Worst Itch NRS ≥ 5) or enter an extended screening period of a no-drug Observation Period (Worst Itch NRS < 5) based on their reported NRS scores on the first Visit (Visit 1a). For up to 12 extended screening weeks, patients in the no-drug Observation Period may also transition into the drug Treatment Period if their Worst Itch NRS increases to ≥ 5 .

To allow for various starting levels of pruritus intensity, patients who have a Worst Itch NRS that is ≥ 5 will enter the Treatment Period upon completion of Visit 1a. Patients whose Worst Itch NRS score is < 5 will be entered into an extended screening period, no-treatment criteria Observation Period for up to 12 weeks or until they develop a higher level of pruritus (i.e., Worst Itch NRS ≥ 5), at which point they will transition to the Treatment Period upon completion of Visit 1b. All patients entering the Treatment Period, whether immediately upon study entry or following a period of time in the Observation Period, will initially be titrated to a dose that can be as high as 180 mg twice daily (BID) during the first 4 weeks of the Treatment Period. Patients who continue in the Observation Period and maintain a Worst Itch NRS score of < 5 will be screen failed from the study at the end of the 12-week period. For enrolled patients whose Visit 1a worst itch NRS score satisfies the ≥ 5 enrollment criterion and for whom treatment is initiated, the screening visit Visit 1a will also be designated as the baseline visit. For enrolled patients who must continue into the Observation Period, the first visit during that period when the worst itch NRS ≥ 5 criterion is satisfied will be designated as Visit 1b and that visit will serve as the baseline visit.

The total study duration for any individual patient will be up to 53 weeks. For patients who enter directly into the Treatment Period, the total amount of time on drug will not exceed 50 weeks. Patients who enter the Treatment Period from the Observation Period, the total amount of time spent in the combined two periods of the study cannot exceed 50 weeks. All patients who received drug treatment will have a 2-week Washout and Safety Follow-up period at the end of the dosing period, unless consent is withdrawn.

The total amount of time in the Observation Period cannot exceed 12 weeks. After these 12 extended screening weeks, patients not eligible for the Treatment Period are screen failed from the study. The study periods are summarized below.

Study Period	Study Weeks	Duration
Observation Period	
Patients who do not meet the criteria to start Treatment are followed in Observation Period visits (OV) for up to 12 extended screening weeks. During this time, the patient may meet criteria and become eligible to enter the Treatment Period. If the patient does not meet the criteria to enter the Treatment Period by the end of 12 extended screening weeks (OV12), participation in the study ends and the patient is screen failed
	Up to 12 Extended Screening weeks
Treatment Period	
For patients directly entering the Treatment Period as of Visit 1a, the Treatment Period begins with Study Week 1 (Visit 1a) and ends with Study Week 50.
 
For patients entering the Treatment Period after being followed in the Observation Period, the number of weeks on treatment and the end of the Treatment Period varies. (See Table 8 in the study protocol for the details of which treatment visits are to take place).
 
The End of Treatment Visit will take place after the patient completes the last week of study drug.
	Up to 50 weeks
Washout and Safety Follow-Up Period	
The Washout and Safety Follow-up Period is two (2) weeks in duration.
 
For patients directly entering the Treatment Period as of Visit 1a and completing 50 weeks of study drug treatment, the Washout and Safety Follow-up Period should take place during weeks 51 and 52.
 
For patients entering the Treatment Period after being followed in the Observation Period, the number of weeks on treatment and the end of the Treatment Period varies; Table 8 in the Study Protocol calculates the Treatment Visit assignments for any patient entering the Treatment Period from the respective Observation Period visits. The Washout and Safety Follow-up Period will take place during the two (2) weeks after the patient completes the last week of study drug.
 
The Washout and Safety Follow-up Period Visit will take place in the week following the completion of the two (2) week Washout and Safety Follow-up Period.
	2 weeks

3.2. Premature Discontinuation of Study Drug Treatment

3.2.1. Premature Discontinuation of Study Drug Treatment Associated with Failure-to-Improve Criterion

Patients who meet failure-to-improve criterion during the conduct of the study, will stop taking study medication.

The Failure-to-Improve criteria are as follows: Beginning on Treatment Period Visit 3 (TV3), and at every subsequent Treatment visit, patients with a worst itch NRS score \geq the worst itch NRS score at Visit 1a (or at Visit 1b in the case of patients who require the OV period) will be discontinued from study drug. Patients discontinued from study drug are to undergo the End of Treatment Visit (TV14), the Washout/Safety Follow-up Period assessment in two weeks, and receive a follow-up telephone contact 30 days following end of study drug dosing for final safety assessment.

3.2.2. Premature Discontinuation of Study Drug Treatment For Reasons Other Than Failure-to-Improve

Patients who complete Study Drug treatment through the End of Treatment Visit 14 (TV14) (even if some doses have been missed or if the patient was followed in the Observation Period before receiving study drug treatment) are considered to have completed Study Drug treatment. Patients discontinuing Study Drug treatment prior to the maximum allowable number of Treatment Weeks (based on their entry into the study at either Visit 1a or Visit 1b) will also be considered to have prematurely discontinued Study Drug treatment. Patients discontinuing Study Drug treatment prior to End of Treatment Visit 14 will be considered to have prematurely discontinued Study Drug treatment and will be asked to complete the End of Treatment Visit (TV14) regardless of where they were in the study visit schedule, the Washout and Safety Follow-up Period Visit and the Premature Discontinuation of Study Drug Telephone Contact visit. Patients removed from the study after enrollment and who have received a dose of study drug will not be replaced.

Some reasons for premature discontinuation of Study Drug treatment include:

- Intercurrent illness
- Any intolerable Adverse Event (AE) that cannot be ameliorated or safely managed with medical intervention or one that poses undue risk to the subject if Study Drug treatment were continued in the opinion of the Medical Monitor or Investigator
- Electrocardiogram (ECG) changes summarized in protocol Section 17.4
- Opioid medication is introduced in anticipation for chronic use of greater than 2 weeks
- Any medication prescribed for chronic anti-pruritic use of greater than 2 weeks
- Development of substance abuse as determined by the Investigator.

